The intervention will be provided in a flexible manner, as determined by the parents' needs, circumstances and preferences and the child's developmental condition. Mothers and fathers will both be encouraged to interact with the coach and seek advice and support. The coach will be reachable at least every second day (minimum 4-6 hours per day, 3 days per week); however, calls with families will vary from a minimum of every 4 weeks (ideally every 2 weeks) and will be scheduled at a time convenient for the parent with evening appointments available until 8 pm at least one night per week. Calls will be audiotaped and reviewed by the study team to ensure program quality and reviewed by peer-coaches for self-review and program quality improvement on an iterative basis. Coaches will receive manuals and specific training activities including small group discussions, experiential learning and sharing of best practices among coaches in the trial. A registered health professional (i.e. experienced social worker and family counsellor with expertise in family/ young child counselling) has been hired as a "Coach Lead" to provide training, mentoring and oversight of coach activities.

In addition to the coach, specific evidence-based *educational web content* will be sourced and curated by the project team and relevant stakeholders (conducted in the first year as part of intervention development). Input and feedback from the parent advisory group will further refine and inform the program content. The content will be linked to an online care coordination platform - the *Igloo platform* - which puts each family at the centre of each network (family, friends, health professionals), and then allows each family network to link with other family networks in the intervention arm of the study. This will enable families the opportunity to find and store resources, create connections with the coach, health providers and other families, thereby creating a network of individuals to support them formally and informally. Peer support (among parents in the intervention arm) will be a critical part of this service delivery strategy, enabling parents to share strategies. This password-protected website will include credible links to sites based on the family-based needs assessment described above.

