Descriptive statistics will be used to characterize our sample in the experimental and control arms. The primary analysis is to ascertain benefit of the BRIGHT system (Coach + online education tools + online peer support) compared to usual care (control) will be between group (intervention vs control) comparison of primary and secondary outcomes using t tests (two-sided, $p<.05$). Statistical comparisons will be made at 8- and 12- months post enrolment, to determine if group differences manifest early and if they continue to improve or stabilize. This will be important in determining whether the BRIGHT system is necessary over a prolonged period (8 vs 12 months) to achieve its goals. Principles of intent-to-treat analysis will be applied. Repeated measures with mixed model analysis will be used to assess effect of group category and province with intervention at two time points. Within the intervention group, predictors of change scores between baseline and outcomes (dependent variable) will be tested to determine which children/families are more likely to be responsive to the BRIGHT system. Multivariate linear regressions will be conducted with independent variables, to include: parent readiness score, sociodemographic factors, child's functioning (Vineland), province, and engagement in the Igloo platform. The structural properties of the network (Igloo) will be analysed using UCINET [17]. Network analysis related to patterns of use of the online platform will be correlated with the outcome measures of interest in this study.

Sample size:

We will recruit 392 participants; we project a sample size of 352 based on: i) two-sided test of the null hypothesis at $\alpha=.05$, ii) $\beta=.80$, iii) 10% attrition; iv) difference of 0.3 SD.

Studies as of yet have not identified a minimal clinically important difference (MCID) for our primary outcome measure (the Family Empowerment Scale) that could be used to estimate sample size calculation. In the absence of a “clinimetric” MCID, a distribution-based methods approach is commonly applied that proposes a fraction of the pooled Standard Deviation (i.e. utilize effect size estimates). In this case, the difference of 0.3 standard deviation can be used to detect modest effects that may be clinically significant; or 0.5 SD for moderate to large effects [18, 19].

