Policy-makers and health/social service administrators: This audience will be a critical audience given the wait-lists and waiting times for developmental services that parents experience. The content for this audience will focus on the nature of the intervention, the key ingredients that showed success, the cost-utility analysis. With respect to tactics, a policy dialogue will be hosted in year 5 and policy options for implementation will be constructed. A policy paper with associated briefing notes (generic), which can be tailored to each province and their relevant ministries, will be created.

Providers: Providers will be interested in these results. The focus with respect to content for this audience is on the effectiveness of the intervention and its relation to “usual care”. Tactics will include peer-reviewed articles and presentation at local, provincial, and national meetings will be undertaken.

PLANS FOR TRAINING

The British Columbia and Quebec recruitment sites have funding to support a doctoral or postdoctoral trainee throughout the duration of the project. The trainees will have the opportunity to expand their knowledge and expertise in health services research, network analyses, family engagement and pragmatic randomized trials. In addition, the trainees will be expected to participate in CHILD-BRIGHT’s patient-oriented training program.

The investigators of our ‘BRIGHT Coaching system’ study will be working collaboratively with investigators from other projects (theme 3 projects, Strongest Families in theme 2) that are applying a coach model to develop a manual. This handbook will describe health coach frameworks and key ingredients of success (from the literature), and define the coach’s roles and responsibilities and provide case examples to further clarify this service delivery approach. Our team will work with the other teams to develop training modules on the coach model, for the benefit of particular stakeholder groups that would be interested in learning more about this model of care. These modules will be tailored to the user (i.e. parents, clinicians, policymakers and health administrators) to promote greater understanding of the benefits and challenges. There will be an interactive component to enable stakeholders across groups to discuss the potential applications of a coach model to support children with disabilities and their families across key transition points of care.

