Anticipated Outcomes:	
 • Parents will be more empowered and knowledgeable, and make more informed decisions about their child's care and development • Services accessed will be appropriate based on the child's and family's needs and developmental services will be more cost-effective • Providers will feel confident that their clients are receiving appropriate services and supports based on client needs
Anticipated Impacts:	
A more responsive health care system that meets the developmental needs of children and the health and knowledge needs of parents.
 
The electronic platform (Igloo) will be tested with respect to its utility as an information and support network, for consideration for other chronic diseases of childhood.

	Research trainees will be well prepared to pursue future child health research with a strong inclusion of families and their support networks.
--	--

TABLE 2. SUMMARY OF MAIN PREDICTOR AND OUTCOME MEASURES

VARIABLES	MEASURE
PRIMARY PREDICTOR	
Intervention versus control group	Randomization to one group
Other Key Variables	
Child's age	Age at recruitment in months to one decimal place
Child's sex	Male/female
Parental involvement in the intervention	Mother vs father; # of uses of Igloo platform (areas: coach, online education tools, peer support)
Socioeconomic factors	Parents' education level, postal code
Readiness for health coach model	Readiness for coaching questionnaire (3-points)

OUTCOMES	
PRIMARY	
Empowerment (ability to manage and take charge) at the family, services and community levels	Family Empowerment Scale
Parental satisfaction and efficacy with competency	Parents Sense of Competence Scale
SECONDARY	
Family stress level	Parenting Stress Index
Parental well-being (quality of life)	SF-36
Family-centered care provided by coach to include educational benefits	Measure of Process of Care

Health service utilization and costs	Resource Utilization Questionnaire (adapted from [name] and [name])
Profile Form	Surveys on background of participant & family structure
Demographic Form	Survey on family socioeconomic status and education level
Child's functional abilities	Vineland
Survey on parent/caregiver mental health	Parenting Morale Index

REFERENCES

1. Majnemer, A., et al., *A new look at outcomes of infants with congenital heart disease*. Pediatric neurology, 2009. **40**(3): p. 197-204.

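### Igloo engagement, chosen by families after randomisation and only in the BRIGHT arm, should not be a predictor of response, and its correlation with outcome cannot show platform benefit

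*Protocol*

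**What the plan says.** The Statistical analyses section of the protocol plans two analyses that involve platform use.

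- **A predictor model.** "Within the intervention group, predictors of change scores between baseline and outcomes (dependent variable) will be tested". The stated aim is "to determine which children/families are more likely to be responsive to the BRIGHT system". The independent variables are to include "parent readiness score, sociodemographic factors, child's functioning (Vineland), province, and engagement in the Igloo platform".
- **A use-outcome correlation.** "Network analysis related to patterns of use of the online platform will be correlated with the outcome measures of interest in this study".

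Other sections show what kind of variable engagement is. Study procedures states: "The intervention will be provided in a flexible manner, as determined by the parents' needs, circumstances and preferences and the child's developmental condition". Table 2 measures involvement as a number of uses of the platform, by area. Under Study procedures, family networks link with others in the intervention arm, and control families get access only once the study is complete. Table 1 says of the platform: "The electronic platform (Igloo) will be tested with respect to its utility as an information and support network". It also lists an evaluation of the platform's value as a Year 5 deliverable. Neither entry names a method.

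The main comparison is between randomised arms, for the whole package of coach, education tools and peer support, on intent-to-treat principles.

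**The concern.** The predictor model places one post-randomisation variable among factors known at entry. This raises three problems.

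1. Engagement cannot tell a service, at the time of referral, which families will respond. If readiness or education works partly by raising engagement, conditioning on engagement also removes that part of their effect.
2. Families who log in more may be more motivated, more in need, or already improving. Any of these links use to outcome without the platform doing anything. The bias can run either way: motivation would tend to make the platform look useful, and need would tend to make it look useless or harmful.
3. A change score in the intervention arm contains natural change and regression to the mean as well as response. The control arm could separate these, but the model leaves it out.

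At stake are the protocol's statement of who responds to BRIGHT and any inference that the platform itself produces benefit.

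**Working it through.** **Plan's own figure.** No number is given for the engagement analyses. The nearest is the sample size, which fixes the size of the BRIGHT arm. For 0.3 SD, two-sided 5% and 80% power, n per arm = 2 × (1.960 + 0.842)² / 0.3² = 174.4, rounded up to 175 (350 in total). The t-test version gives 350.8 in total, so 176 per arm and 352. Dividing by 0.9 for attrition gives 352 / 0.9 = 391.1, so 392. The stated 352 and 392 reproduce. With 1:1 allocation, 176 BRIGHT families are analysed. If only 350 are recruited, a figure the protocol also gives, 175 × 0.9 = 157.5 remain.

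**Arm-only change scores.** Let X be a baseline factor with slope γ on change under usual care and γ + δ under BRIGHT. Response is about δ. The intervention-arm regression estimates γ + δ. Only a comparison with the control slope isolates δ.

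**Engagement in the model.** Suppose X raises engagement by a per unit, engagement raises change by b, and X also acts directly by c. The total effect of X is c + a × b. With engagement in the model, the coefficient of X targets c alone. If an unmeasured trait also drives both engagement and change, even c is not recovered, because conditioning on engagement links X to that trait.

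**Use-outcome correlation.** This is an illustration under assumptions, because the documents give no correlations. Let use have no effect, and let one unmeasured trait correlate r with use and r with change. The expected use-change correlation is then r × r. It is significant at 5% when it exceeds t / √(n − 2 + t²), which is 0.148 for n = 176. Results of 5,000 simulated trials per cell:

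| Assumed r | Expected spurious correlation | p < .05, n = 176 | p < .05, n = 157 |
|---|---|---|---|
| 0 | 0 | 4.8% | 4.8% |
| 0.2 | 0.04 | 7.5% | 7.6% |
| 0.3 | 0.09 | 21.5% | 19.9% |
| 0.4 | 0.16 | 56.4% | 51.0% |
| 0.5 | 0.25 | 92.3% | 89.5% |

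If the trait raises use but goes with less improvement, as need might, the expected correlation is −r × r. By symmetry the rejection rates are the same, with the opposite sign. The table is for an unadjusted correlation; adjustment for readiness and other baseline factors would reduce the bias by an unknown amount.

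**The case against.** The defence has real strength. The section speaks of correlation and predictors and claims no causal effect of use. The covariate list is open and already holds readiness, a partial proxy for motivation. Adjustment of the network correlation is neither stated nor excluded, and such detail may sit in an analysis plan that is not shown. The efficacy claim attaches to the randomised package. These points stand, and they confine the matter to secondary analyses. They do not rescue the predictor model: the protocol itself names engagement as an independent variable, restricts the model to one arm and gives the aim of finding responsive families.

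A reader might infer more than the documents support:

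- **That the ingredients message would rest on these correlations.** The policy-maker plan speaks of "the key ingredients that showed success", but the section on the additional qualitative study assigns key ingredients to exit interviews.
- **That the platform's value would be judged only on these correlations.** Table 1 names no method, and the outcome-measures section also evaluates the platform by utilisation and satisfaction surveys.
- **That a spurious correlation would be presented to policy makers as proof that the platform works.** The knowledge-translation plan does not mention the use-outcome correlation.
- **That the false-positive rate is known to be high.** The trait correlations are assumed, and at 0.2 the rate is only 7% to 8%.

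**Conclusion.** The concern holds for two things: the predictor-of-response model, and any inference of platform benefit drawn from the use-outcome association. Engagement does not belong beside baseline factors in a model meant to identify responders, and the use-outcome association has no randomised contrast behind it. These conclusions rest on the protocol's description of engagement as chosen by the family, counted after randomisation and confined to one arm. They need no numerical assumption. The size and direction of the bias do need one, and the documents do not supply it; the simulated rates only show that moderate confounding would be enough to mislead. The randomised intent-to-treat comparison, its error rate and its sample size are untouched. This should be corrected, but it does not threaten the main result.

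**What to change.** Amend the Statistical analyses section as follows.

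- Remove Igloo engagement from the predictor-of-response model.
- Restrict predictors to baseline variables: readiness, sociodemographic factors, Vineland and province. Test each as a treatment-by-covariate interaction using both arms, with the baseline score as a covariate.
- Report any use-outcome association separately, as exploratory and descriptive. Adjust it for the baseline score and baseline covariates, but not for the 8-month score, which is itself downstream of use.
- State that platform efficacy is not inferred from that association.

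No new data are needed; the change costs wording and some analyst time. The scientific price is weaker claims about the platform and limited power for the interactions. For example, with 352 analysed and a baseline factor that splits each arm in half (88 per cell), the standard error of the interaction is √(4/88) = 0.213 SD, against √(4/352) = 0.107 SD for the main effect. The interaction detectable with 80% power is therefore about 2.80 × 0.213 = 0.60 SD, twice the planned 0.3 SD, before any gain from adjusting for the baseline score. The interaction results should be presented with intervals and as exploratory.

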Eligible children and their families will be recruited to include preschool children 1.5-4.5 years (18 to 54 months) at the age of enrolment, who are not expected to enter school/kindergarten within 6 months of enrolment. Children will be living in four diverse parts of Canada to ensure national representation and future scalability: British Columbia, Manitoba, Nova Scotia, Quebec. Participants' postal codes will be analyzed to ensure representation: rural/remote, small urban and large urban/metro representation with purposeful sampling as required. From the patient population perspective, two different groups that are likely to manifest new global developmental delays at this stage will be recruited. They are at high risk for brain-based developmental delays, however some will have no delay and others will have mild, moderate or severe delays.

Children at risk who are not yet receiving developmental services: Primary care provider and/or parental concerns regarding their child's developmental progress become apparent in the preschool years.

Inconsistent use of screening tools and variation in triage and assessment methods often result in delayed detection and long wait lists for services. Children will be those waiting for their first formal appointment for diagnosis and assessment for “developmental delay”, from a public health facility, a child developmental centre and/or a dedicated hospital clinic. These children represent a group who are not currently receiving developmental services. These children may be found to have no delay, a delay in one domain (e.g. specific language impairment) or global delays, which can be mild to severe. This will be a consecutive sample on the wait list and who are between 1.5-4.5 years of age.

For this trial, children/families will be excluded if they: (1) are non-English speaking (and non-French speaking in sites where services are available in French); (2) are unwilling or unable to meet with the study team for intermittent assessments; (3) do not have access on a routine basis to the internet through a desktop or mobile device. We will recruit 350 subjects, 175 for both intervention and control arms.

Study procedures: Intervention and control

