We aim to recruit a sample of 350 participants (randomized to either intervention or control group) across the four sites. This will be approximately 100 from British Columbia, 100 from Quebec, 75 from Manitoba and 75 from Nova Scotia. In order to be able to detect modest effects that may be clinically important (0.3 SD), this would require recruitment of a sample of 392, accounting for 10% attrition, for a sample of 352. Furthermore, this larger sample size would enable us to account for cluster randomization. We expect that all participants are independent, whether or not they live in any of the provinces. Nonetheless, it is conceivable that the association within provinces is slightly stronger (weak ICC=0.100) than the association between participants across provinces, due to environmental context (i.e. different health care and social service systems). A sample size of 346 (recruit 384, 10% attrition) would allow us to account for cluster randomization. We will apply a linear mixed model to account for the possible effect of province on the benefits of treatment on empowerment and parent competency.

PLANS FOR KNOWLEDGE TRANSLATION

The results of this study will be relevant to families, health service administrators, policy makers and providers.

Families: Families will be important consumers of the results of this study. In order to determine how best to communicate the results to them, a focus group of families will be brought together. They will guide strategy and tactics with respect to the study results. The content for this knowledge translation will be particularly focussed on the benefits and challenges from the perspective of families. With respect to tactics, it is anticipated that family councils, childhood-disability focussed organizations, the media, family-guided web-based materials and providers will be modalities undertaken to reach families. This plan will be modified subsequent to the focus group with families after the conclusion of the study.

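### The protocol commits to recruiting both 350 and 392 families (and floats 384); the 80% power at 0.3 SD was worked out for 392, and 350 gives about 76%

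*Protocol*

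**What the plan says.** All the relevant text is in the protocol, in three places.

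- **Participants:** "We will recruit 350 subjects, 175 for both intervention and control arms".
- **Sample size, opening sentence:** "We will recruit 392 participants; we project a sample size of 352 based on" a two-sided 5% test, 0.80 (printed as beta, evidently meaning power), 10% attrition and a "difference of 0.3 SD".
- **Sample size, last paragraph:** "We aim to recruit a sample of 350 participants (randomized to either intervention or control group) across the four sites", followed by "This will be approximately 100 from British Columbia, 100 from Quebec, 75 from Manitoba and 75 from Nova Scotia". The next sentence returns to the larger total and says of 0.3 SD that "this would require recruitment of a sample of 392, accounting for 10% attrition, for a sample of 352". The paragraph then says that this larger sample would also cover clustering, introduces a province ICC of 0.100 as a possibility, and ends with a third pair: "A sample size of 346 (recruit 384, 10% attrition) would allow us to account for cluster randomization".

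The Statistical analyses section names two-sided t tests between arms as the primary analysis. The section on study procedures describes 1:1 randomisation of participants, stratified by site.

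**The concern.** The statements for 350 in Participants and for 392 at the head of Sample size are both unconditional, and both concern the number to be recruited. They cannot both be the target. The last paragraph of Sample size repeats each of them without choosing.

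The choice matters because the power statement is attached to one total and the operational numbers to the other. The 80% power belongs to 392 recruited and 352 evaluable. The per-arm number and the site targets belong to 350. Sites following the only targets they are given would stop 42 families short of the number the protocol says 0.3 SD requires. The total also fixes when recruitment is complete, and it is the planned figure against which achieved enrolment will later be reported.

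The 384/346 pair adds confusion. No calculation is shown for it, and its reference to cluster randomisation does not fit the individual, site-stratified randomisation described elsewhere in the protocol.

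**Working it through.** **Inputs, all from the protocol:** standardised difference d = 0.3; two-sided alpha 0.05; power 0.80; 10% attrition; 1:1 allocation; unadjusted two-sample t test; recruitment totals 350, 392 and 384.

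**1. Reproducing the plan's own figure**

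- Normal approximation: n per arm = 2 × (1.960 + 0.842)² / 0.3² = 174.4, rounded up to 175, or 350 in total.
- Exact t test: 175.4 per arm, rounded up to 176, or 352 in total. This is the protocol's evaluable number.
- Attrition: 352 / 0.9 = 391.1, rounded up to 392 (196 per arm). This is the protocol's recruitment number.

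So 352 and 392 are correct for the stated assumptions.

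**2. Checking the other totals**

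- Site targets: 100 + 100 + 75 + 75 = 350.
- Third pair: 384 × 0.9 = 345.6, or 346. The pair is consistent with 10% attrition, but the origin of 346 is not shown.

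**3. Power for each total after 10% attrition**

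Power comes from the noncentral t distribution with noncentrality d × √(N/4), where N is the evaluable total. For 350 recruited, N = 350 × 0.9 = 315 and the noncentrality is 0.3 × √78.75 = 2.66.

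| Recruited | Evaluable | Power at 0.3 SD | Difference with 80% power |
|---|---|---|---|
| 392 | 352.8 | 80.2% | 0.299 SD |
| 384 | 345.6 | 79.4% | 0.302 SD |
| 350 | 315 | 75.6% | 0.317 SD |

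The normal approximation for 315 gives 75.9%, so the answer is about 76% either way.

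**4. Sensitivity of the 350 figure to attrition**

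- No loss (350 evaluable): 79.9%.
- 5% loss (332.5 evaluable): 77.9%.
- 10% loss (315 evaluable): 75.6%.

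**5. Sensitivity to adjustment for province**

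Assume that the protocol's ICC of 0.10 is the province share of total variance, and that individuals are randomised within site. Adjustment then leaves a residual variance of 0.90, and the effective difference is 0.3 / √0.90 = 0.316. With 315 evaluable the noncentrality is 0.316 × √78.75 = 2.81, and power is 79.9%.

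**6. Size of the discrepancy**

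392 − 350 = 42 families. That is 42/392 = 10.7% of the larger total, or 42/350 = 12% above the present site targets.

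**The case against.** Four points can fairly be made for the plan.

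*There are really two competing targets, not three.* The 384/346 pair is conditional and attached to a possibility, and nothing says that 384 will be recruited. This stands, and the pair is a side issue. A smaller number under a province model is not in itself an error either: with randomisation within site, removing between-province variance lowers the required number. What remains is that 346 has no shown derivation and that the cluster wording does not match the design.

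*The 350 may be the evaluable number, mislabelled.* The normal approximation gives exactly 175 per arm and 350 in total before attrition, which matches the Participants section. This is plausible. But the text uses the word recruit for 350 in both places and splits it by arm in one and by site in the other. If it is a mislabelled evaluable number, Participants and the site targets omit the attrition allowance, and the same correction is needed.

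*The 76% is only one branch.* This is correct. The per-arm and per-site breakdown points towards 350 and the flat statement at the head of Sample size points towards 392, so the document does not settle the matter. If 392 governs, power is as stated.

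*The loss is small and may be nil.* The protocol also plans a linear mixed model for province effects on empowerment, and with that adjustment 315 evaluable would give about 80%. This stands as a limit on the consequence. But the t test is the analysis named as primary, and the conflict between totals remains whatever the power.

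**Conclusion.** The concern holds. The protocol states two incompatible recruitment totals, 350 and 392, and does not say which governs; a conditional 384 adds to the confusion. The 80% power at 0.3 SD was calculated for 392 recruited and 352 evaluable, and that calculation is right. If 350 is the real target, power under the unadjusted t test is 75.6% with the protocol's own 10% attrition, and 80% power is reached at 0.317 SD rather than 0.3 SD.

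The power shortfall is modest, at most about 4 points. It depends on 350 governing, on 10% attrition and on an unadjusted analysis; with lower attrition or with province adjustment at ICC 0.10 it shrinks or disappears. The inconsistency in the totals depends on none of these and should be corrected.

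**What to change.** Choose one recruitment total and use it in Participants and throughout Sample size. First establish whether 350 was meant as the number before the attrition allowance.

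- **If 350 is kept:** state 350 recruited, 315 evaluable after 10% attrition, and about 76% power for 0.3 SD (80% for 0.32 SD) with an unadjusted t test. Remove or reconcile both 392/352 and 384/346. This is a wording change only, at the price of a slightly less favourable power statement.
- **If 392 is chosen:** change the Participants total to 392 and the per-arm number to 196, and revise the site targets. A pro rata split is 112, 112, 84 and 84, which sums to 392. Remove or reconcile 384/346. The cost is 42 more families than the present site targets, or 12%.

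In the same edit, write power (1 − beta) = 0.80 in place of beta = 0.80. That is a notation slip and does not affect the calculation.
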